4.2 SCIENTIFIC RATIONALE FOR STUDY DESIGN

We elected to approach this problem in a retrospective fashion due to the availability of existing data that is likely sufficient to answer our clinical question and the known risks of radiation from CT exposure. Many asthmatics undergo CT scans for various reasons; however, it is rare to obtain a CT scan in a stable asthmatic, even if symptoms are severe, since there is no known current clinical utility in this diagnostic test. Since our question relies on using CT data to assess body composition in severe asthmatics requiring biologics to find novel parameters that may be able to predict response more reliably than the current standard of care options (FeNO, sputum/serum eosinophils, and IgE), it follows that utilizing existing CT data while also having the concurrent retrospective benefit of known response to biologic therapy would allow this question to be most efficiently addressed without exposing any of the subjects to the harms of radiation solely for research purposes. Furthermore, our use of a learning cohort retrospectively constructed at the University of Michigan and a prospectively constructed validation cohort from the University of Calgary will allow us to generate more robust results than normally found in retrospective studies since we will be using a geographically distinct validation model.

5 STUDY POPULATION

5.1 INCLUSION CRITERIA

Our population will include all adults 18 years or older with a diagnosis of asthma (defined as a positive methacholine test, supportive PFTs, or clinician diagnosis with appropriate supporting clinical context) who have been prescribed and taken an FDA-approved biologic medication for severe asthma (mepolizumab, benralizumab, reslizumab, omalizumab, or dupilumab) and have chest CT images in the University of Michigan radiology databases. All patients from the Calgary cohort will be screened in a similar fashion.

5.2 EXCLUSION CRITERIA

We will exclude patients with a > 10 pack year history of smoking and those with evidence of emphysema on CT imaging due to concerns that concurrent COPD may be attenuating the effects of the biologic. Those with some scattered bronchiectasis thought to be secondary to severe asthma will not be excluded; however, severe bronchiectasis secondary to other causes will be excluded for the same reason. Furthermore, patients who do not have accessible adequate follow-up information (4 or more months from drug initiation with clear documentation of response) will be excluded from the final analysis in part 3 due to an inability to assess response but will be included in the initial analysis to help with cluster identification.

6 STATISTICAL ANALYSES

6.1 BASELINE DATA ANALYSIS

Tabulate summary statistics of baseline characteristics for each analysis cohort. Continuous variables will be summarized using mean, median, standard deviations, and interquartile range (IQR) of each baseline characteristic. Categorical variables will be summarized using class percentages. Perform exploratory data analysis (EDA) to identify potential outliers, assess the statistical distribution of data elements (e.g., Normal vs. Chi-square), and examine bivariate correlation matrix for potential non-linearity. Compare pre-treatment characteristics of University of Michigan and University of Calgary cohorts to assess similarity using Student's t (continuous, Normal), Fisher's Exact (binomial), Wilcoxon rank-sum (continuous, non-Normal), and Chi-Square/Tukey's Honest Significant Difference (Categorical) statistical tests.

6.2 MORPHOMICS ANALYSIS AND PHENOTYPING

Compute height-normalized measures to control for height-related correlation, e.g., Skeletal Muscle Index = (Skeletal Muscle Area / Height²). Center and scale morphomics measures into standard deviation units, stratified by sex, to control for sex differences. (Optionally/additionally, convert morphomics measures into sex- and age-adjusted percentiles using the Reference Analytic Morphomics Population (RAMP), to simultaneously control for sex- and age-related correlation). The following analyses will be performed on both the UM and UC cohorts combined. Classification and regression tree (CART) will be utilized to develop individualized decision rule on SARP class based upon morphomic measures. In addition, Unsupervised learning techniques will be carried out to identify novel clusters for morphomic phenotypes in these cohorts.

6.3 IDENTIFICATION OF BIOMARKERS FOR OUTCOMES

To incorporate high-dimensional morphomic parameters to better stratify patients in regard to their probability of complete response, we will leverage the regularization technique in machine learning to select important variables and develop risk predictive models. To be more specific, elastic net regularization will be utilized to address the high dimensional nature of data derived with analytic morphomics. Elastic net consists of a linear combination of L1 (lasso) and L2 (ridge) penalty to address over-fitting and co-linearity, respectively. In addition, to capture potential non-linear effects among variables, we will also apply random forest and gradient boosting, two highly utilized ensemble tree-based methods. Sample splitting will be used to assess model performance. We will evaluate the accuracy of developed predictive models by various performance measures, including Harrell's Concordance index, integrated cumulative area under the curve, and integrated brier score. The final developed predictive model will be evaluated on an independent dataset from the University of Calgary.

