Secondary Objectives:	
1. To identify imaging biomarkers that are associated with the probability of any post-treatment improvement of FEV1 of 5% or more2. To identify imaging biomarkers that are associated with the probability of any post-treatment reduction in maintenance OCS use							
Exploratory Objectives:	
1. To identify imaging biomarkers that are associated with the probability of any reduction in pre-treatment baseline hospitalizations for asthma2. To identify imaging biomarkers that are associated with the probability of any post-treatment improvement in ACT score3. To identify imaging biomarkers that are associated with the probability of any subjective post-treatment reduction in symptoms described clinically							
Endpoints:	Primary Endpoint:	Determine the cutoff value in chest wall muscle size/quality that optimally classifies patients that had and did not have any reduction in pre-treatment baseline exacerbation frequency (binary). Alternative (continuous): determine the strength of the linear/non-linear relationship						

	between continuous chest wall muscle size/quality and continuous change in exacerbation frequency
Secondary Endpoints:	
 1. Determine individual and combinations of body composition measures (phenotypes) associated with a 5% or greater improvement in FEV1 when compared to baseline FEV1 2. Determine individual and combinations of body composition measures associated with any reduction in maintenance OCS use when compared to baseline OCS use
Exploratory Endpoints:	
These endpoints may be limited in scope of analysis by the sample size within each of the outcome groups.
 
 1. Determine individual and combinations of body composition measures associated with any reduction in hospitalizations when compared to baseline hospitalizations 2. Determine individual and combinations of body composition measures associated with any improvement in ACT score when compared to baseline ACT score 3. Determine individual and combinations of body composition measures associated with any subjective improvement of symptoms when compared to baseline symptoms

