2 INTRODUCTION

2.1 STUDY RATIONALE

DISEASE BURDEN IN SEVERE ASTHMA AND THERAPY SELECTION

Asthma is a highly prevalent disease that affects 33 million people in the United States and Canada. The vast majority of asthma patients are well controlled with conventional asthma therapies; however, 10% of patients have severe disease that is associated with significant comorbidity and exposure to high doses of OCS. OCS use increases the odds of developing comorbid diseases such as diabetes, hypertension, cardiac disease and cataracts and is increasingly being recognized as a major contributor to severe asthma costs, making the development of alternative less harmful therapies paramount¹. Fortunately, over the past three years there has been a rapid increase in the number of biologics approved for the management of severe asthma with type II inflammation, which is estimated to be present in up to 60% of this population. The term type II inflammation refers to an increase in the levels of type II cytokines including IL4, IL5 and IL13, which induce pathologic downstream production of IgE and eosinophils. Current clinical practice utilizes surrogate biomarkers, including peripheral and sputum eosinophils, FeNO and total IgE levels, to phenotype patients with severe asthma and guide biologic drug selection. Unfortunately, these surrogates are imperfect and prone to error from multiple sources, especially in the obese².

Unequal Response to Therapy Despite Similar Biomarkers

The response to targeted biologic therapies is heterogeneous despite the use of well-studied biomarkers to select potential responders. Unfortunately, even when patients with a high likelihood of response are selected, 10-15% have complete non-response in all clinical parameters, and only 40% have a robust and complete response to therapy. This is likely related to the presence of overlapping inflammatory pathways, co-morbid eosinophilic diseases that affect response to therapy, possible sub-optimal dosing of drug and the lack of highly specific biomarkers. Precision medicine approaches to severe asthma are in their infancy and the application of complex techniques to help guide therapy are urgently needed. Currently, patients that are partial responders or non-responders to given therapies are switched between available biologics as a means of identifying the best therapy—an inefficient approach that is both time consuming and costly to patients and payers (**Figure 1**).

[figure not shown]

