4 STUDY DESIGN

4.1 OVERALL DESIGN

Over an 18-month period we plan to conduct our study in 3 parts as identified in the study timeline table above.

University of Michigan Cohort Discovery, Database Construction, and Baseline Analysis

We plan to utilize existing data analytic tools at the University of Michigan to search the EMR for eligible patients to include in a retrospective cohort as identified by the inclusion criteria in section 5. We estimate that approximately 300 subjects will meet our initial criteria based on a preliminary search. We will then abstract all available clinical information from the EMR, de-identify it (with coded key stored in a separate, secured location), and enter the resulting coded data into a database. Up to 2 years prior to biologic initiation or CT scan (whichever is earlier) and all post-biologic therapy information will be included. Clinical information we will abstract will include demographic information, heights, weights, comorbid illnesses (coded as malignancy, coronary artery disease, diabetes, stroke/TIA, cirrhosis, and CKD), non-biologic asthma medication dosage and frequency of use (OCS, ICS, SABA, LAMA, LABA, montelukast, zileuton, and theophylline), asthma biologic agent (benralizumab, reslizumab, mepolizumab, omalizumab, and dupilumab) start and (if applicable) end dates as well as reason for end date (coded as ineffective, cost, intolerance/allergy, non-compliance, lost to follow-up, and other), FeNO, ACT scores, serum and sputum eosinophil counts, IgE, pulmonary function test parameters (% predicted), hospital/emergency room/urgent care/unscheduled office visits and phone call encounters for asthma or breathing-related complaints, and subjective clinician assessment of asthma control (independently graded by 2 different clinicians interpretation of EMR data). Each subject will also be assigned a phenotype by the Severe Asthma Research Program criteria¹⁵. If a majority of subjects are missing post-bronchodilator data and unable to be clustered by these criteria, we will instead assign adopted clusters from this paper as follows: Cluster 3-Normal FEV1 ($\geq 68\%$ of predicted), eosinophils (< 200 cells/ μL), FeNO (< 25 ppb), and IgE (< 200 UI/ml) and no evidence of atopy; Cluster 4-Reduced FEV1 ($\leq 68\%$ of predicted) with abnormal elevation of eosinophils, FeNO, or IgE and/or evidence of atopy; Cluster 5--Reduced FEV1 ($\leq 68\%$ of predicted) with normal eosinophils, FeNO, or IgE and no evidence of atopy. We do not expect to have any Cluster 1 or 2 patients in our study but will assign them accordingly if present. We will perform similar abstraction procedures for approximately 200 patients in the University of Calgary cohort, and label the data with a tag for this cohort for analytical purposes.

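### Baseline OCS is abstracted but not specified as an input to the outcome models, so a body composition marker may partly stand in for steroid exposure, most clearly for the maintenance OCS endpoint

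*Combined protocol and SAP*

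**What the plan says.** - **Outcome models (section 6.3).** The stated purpose is "To incorporate high-dimensional morphomic parameters to better stratify patients in regard to their probability of complete response", and the elastic net is to "leverage the regularization technique in machine learning to select important variables and develop risk predictive models". Random forest and gradient boosting are added. There is no list of candidate predictors, no forced-in term and no clinical-only comparator.
- **Endpoints (section 1.1).** The primary endpoint is a single-marker task: "Determine the cutoff value in chest wall muscle size/quality that optimally classifies patients that had and did not have any reduction" in exacerbation frequency. The OCS endpoint reads "Determine individual and combinations of body composition measures associated with any reduction in maintenance OCS use when compared to baseline OCS use".
- **Stated controls.** Section 6.2 begins "Compute height-normalized measures to control for height-related correlation", scales by sex, and makes age adjustment optional. Section 4.1 scales by sex and age. Steroid exposure appears in neither place.
- **OCS data.** Section 4.1 abstracts "non-biologic asthma medication dosage and frequency of use (OCS, ICS, SABA, LAMA, LABA, montelukast, zileuton, and theophylline" and similar data for Calgary, with a look-back of "Up to 2 years prior to biologic initiation or CT scan (whichever is earlier". Section 6.1 only tabulates, explores and compares baseline characteristics.
- **OCS inside the outcomes (section 4.1).** A temporary OCS increase of at least 3 days counts as an exacerbation. In Table 1 an OCS responder has any decrease, and no change means non-responder.
- **Population (section 2.1).** "10% of patients have severe disease that is associated with significant comorbidity and exposure to high doses of OCS".

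**The concern.** OCS exposure could lie on both sides of these models. It may be associated with less muscle or more fat on CT, and it marks severity, which may affect the chance of response. A model that sees only body composition would then credit the marker with information that belongs to OCS.

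This matters because the protocol aims at new markers that outperform existing ones (section 4.2) and suggests a mechanical role for the chest wall (section 2.2). A stand-in for a dose already in the chart would serve neither aim. If the same OCS and muscle relation holds in Calgary, external evaluation may not reveal the problem.

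For the maintenance OCS endpoint the link is structural. A patient on no maintenance OCS has nothing to reduce, yet no section limits that endpoint to baseline users. Any marker that separates users from non-users will then appear to predict OCS reduction.

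**Working it through.** The plan has no power or effect-size figure to reproduce. The 300 and 200 are availability counts.

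**Inputs from the documents.** About 300 Michigan patients, about 200 Calgary patients and about 15% non-response (section 4.1). Expected non-responders: 300 × 0.15 = 45 and 200 × 0.15 = 30.

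**Assumptions, not in the documents.** A share p = 0.3 or 0.5 is on maintenance OCS. Muscle is lower by d = 0.3, 0.5 or 0.8 SD in users. Non-response is 25% in users versus 10% in non-users, or 20% versus 12%. Muscle has no effect given OCS. Overall non-response is then 14.4% (0.3 × 0.20 + 0.7 × 0.12) to 17.5% (0.5 × 0.25 + 0.5 × 0.10), close to the protocol's 15%.

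**Step 1: exacerbation-type endpoint, OCS omitted.** Let q1 and q0 be the shares of OCS users among non-responders and responders. For a normal marker, AUC = 0.5 + (q1 − q0) × [Φ(d/√2) − 0.5].

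- Weakest setting (p = 0.3, d = 0.3, 20% v 12%): q1 = 0.060/0.144 = 0.417; q0 = 0.240/0.856 = 0.280; Φ(0.212) = 0.584; AUC = 0.5 + 0.136 × 0.084 = 0.51.
- Strongest setting (p = 0.5, d = 0.8, 25% v 10%): q1 = 0.125/0.175 = 0.714; q0 = 0.375/0.825 = 0.455; Φ(0.566) = 0.714; AUC = 0.5 + 0.260 × 0.214 = 0.56.

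Large-sample simulation of all 12 settings gives an odds ratio for non-response of 1.04 to 1.22 per SD lower muscle. With OCS in the model it is 0.99 to 1.02.

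**Step 2: the same settings at trial size** (logistic model, two-sided 5% Wald test). The null marker is significant in about 5% to 22% of runs at n = 300 and about 5% to 20% at n = 200. A repeat run put the upper ends at 23% and 17%. Significance in both cohorts in the worst setting is about 0.23 × 0.17 = 4%.

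**Step 3: OCS as a continuous exposure** (15% non-response, 2,000 runs per cell, n = 300).

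| OCS–muscle correlation | OCS odds ratio per SD | OCS omitted | OCS included |
|---|---|---|---|
| 0 | 1.5 to 2.5 | 4.6% to 5.9% | 4.5% to 5.9% |
| −0.2 | 1.5 | 7.8% | 5.3% |
| −0.3 | 2.0 | 22.2% | 4.4% |
| −0.5 | 2.5 | 72.9% | 4.4% |

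Over all cells, including OCS gives 4.4% to 5.9% at n = 300 and 3.9% to 5.8% at n = 200. The Step 1 assumptions imply correlations of 0.14 to 0.37 in size and OCS odds ratios of 1.3 to 1.7 per SD, so the last row lies outside them.

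**Step 4: maintenance OCS endpoint.** Add the assumption that half of users reduce, and grade non-users as non-responders. All responders are then users. Users make up 0.5p/(1 − 0.5p) of non-responders: 0.15/0.85 = 0.176 for p = 0.3, and 0.25/0.75 = 0.333 for p = 0.5. AUC = 0.5 + (1 − share) × [Φ(d/√2) − 0.5].

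- Lowest (p = 0.5, d = 0.3): 0.5 + 0.667 × 0.084 = 0.56.
- Highest (p = 0.3, d = 0.8): 0.5 + 0.824 × 0.214 = 0.68.

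Here lower muscle appears to favour response, the opposite direction to Step 1, although it has no effect. Among baseline users only, the between-group term vanishes and the AUC is 0.50.

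**The case against.** **Silence is not exclusion.** A reader might infer that the plan keeps OCS out of the models. The text does not say so: section 6.3 lists no candidates, and selecting important variables is compatible with clinical ones entering. This stands, so the point is that OCS is not specified. The endpoint wording still points to body composition alone, and an elastic net may drop a penalised OCS term in favour of its correlates.

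**The effect is small and assumed.** A reader might infer that muscle will predict non-response purely through steroids and that Calgary cannot show otherwise. The documents do not support that. Section 2.1 names diabetes, hypertension, cardiac disease and cataracts as consequences of OCS, not muscle or fat change, and nothing says OCS users respond less often. An AUC of 0.51 to 0.56 is near chance, and significance in both cohorts would be rare. This stands for the exacerbation endpoint, but does not remove the structural problem in the OCS endpoint.

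**Prediction does not need confounder control.** A proxy can predict validly, and the objectives speak of association. That is fair, but the claim of novelty makes added value over chart data the relevant question.

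**Why OCS alone?** Baseline exacerbations limit the room to improve on the primary endpoint more directly, and section 4.2 benchmarks against FeNO, eosinophils and IgE. This stands. Requiring a marker to beat an OCS-only model has no basis in the documents; a broader clinical comparator does.

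**Dose may miss the exposure.** Baseline covers the year before initiation, while section 4.1 sets no limit on how early the pre-biologic CT may be, so the dose can postdate the scan. This stands, and is why cumulative OCS is wanted where available.

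**Conclusion.** The concern holds in a limited form. OCS is collected, sits inside two of the outcomes and is not specified as a predictor or adjustment term, while height, sex and, at least optionally, age are controlled.

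For the exacerbation endpoint the possible distortion is modest under the assumptions shown, with a false-positive rate of about 5% to 22% at n = 300. It disappears if OCS and muscle are uncorrelated. The far higher rates in Step 3 need stronger links than those assumptions imply and should not be read as expected. Calgary may fail to reveal the problem if the same relation holds there; the documents do not show that it does.

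For the maintenance OCS endpoint the distortion is larger, AUC 0.56 to 0.68 for a marker with no effect, and comes from who was able to reduce. The figure assumes 30% to 50% users, half of them reducing, and a literal reading of Table 1. A covariate alone does not cure it; the denominator must change too.

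**What to change.** 1. In section 6.3, for the primary and both secondary endpoints, add baseline maintenance OCS (use and dose, plus cumulative OCS over the look-back where available) as an unpenalised term in the elastic net and as a candidate in the tree models.
2. Report each selected marker, and model performance in Michigan and in Calgary, with and without OCS.
3. Set beside these a comparator model of baseline clinical variables already abstracted, including OCS, exacerbations, FeNO, eosinophils and IgE. Describe a marker as adding to clinical data only where it improves on that comparator.
4. Analyse the OCS-reduction endpoint only in patients on maintenance OCS at baseline, and say so beside Table 1.

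**Cost.** SAP wording; the variables are already to be abstracted. It spends a few model terms against about 45 expected non-responders in Michigan. The OCS endpoint loses denominator: at the assumed 30% to 50% use, 90 to 150 of 300 patients in Michigan (300 × 0.3 to 300 × 0.5) and 60 to 100 of 200 in Calgary. Apparent marker effects may shrink, and some confounding may remain where the scan predates the recorded dose.

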
For the purposes of our analysis, we will define baseline measurements as the average of all data obtained in the year prior to biologic initiation or, if only one clinical encounter (defined as an office or emergency room visit) is available in this time period, then the average of the 2 clinical encounters immediately prior to biologic initiation will be used with the time frame noted in the database. In order to assess our primary and secondary outcomes we will use the average of all data from 4 to 18 months after biologic initiation or, if only one clinical encounter is available in this time period, the average of the 2 clinical encounters closest to, but not before 4 months after, biologic initiation. If a second biologic is introduced or the initial biologic choice is

changed, we will use all clinical data prior to the change, even if it is before 4 months of use, then follow the above steps to collect new outcome data on the new drug (see **Figure 4**).

[figure not shown]

Figure 4. Baseline and Response Clinical Data Plan.

Since our interest is primarily in finding the ~15% of patients who do not respond to biologics, we have chosen to include partial and complete responders together in our endpoints in order to isolate the non-responder population. Table 1 below will represent the dichotomization of responders and non-responders for each endpoint using the baseline and post-biologic data as detailed above. An exacerbation will be defined as any hospitalization, urgent care, emergency room, or unscheduled office visit for asthma or a breathing-related complaint or a temporary increase of OCS or ICS dosing for 3 or more days with the intent of the increase to treat acute symptoms. For clinician response, clinical encounter notes will be read and interpreted by 2 independent physicians and graded as detailed in the table. Upon completion of all data abstraction the patient will be de-identified as described in data handling below.

	Responder	Non-responder
Exacerbations	Any decrease from baseline	No change from baseline
Hospitalizations	Any decrease from baseline	No change from baseline
Maintenance oral corticosteroid (OCS) use	Any decrease from baseline	No change from baseline

Change in FEV1	$\geq 5\%$ improvement from baseline	<5% improvement from baseline
ACT score	≥ 1 -point improvement from baseline	No change from baseline
Clinician impression of response to therapy	Any improvement in symptoms from baseline	No change from baseline

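### Section 6.3 aims its prediction models at an undefined complete response, against the any-reduction endpoint, and names two time-integrated accuracy measures although no endpoint has an event time

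*Combined protocol and SAP*

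**What the plan says.** Section 6.3 is where the elastic net, random forest and gradient boosting models are specified. It gives their purpose as to "better stratify patients in regard to their probability of complete response". On accuracy it says "We will evaluate the accuracy of developed predictive models by various performance measures" and then lists Harrell's concordance index, "integrated cumulative area under the curve, and integrated brier score".

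The rest of the plan describes a different outcome. The synopsis and section 3 define the primary endpoint as any reduction in exacerbations from baseline. Section 4.1 explains that the study mainly wants to find the roughly 15% who fail to respond, and draws this consequence: "we have chosen to include partial and complete responders together in our endpoints in order to isolate the non-responder population". It adds that "Table 1 below will represent the dichotomization of responders and non-responders for each endpoint". In that table the non-responder column reads "No change from baseline" in five of the six rows. The FEV1 row reads "<5% improvement from baseline".

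Outcomes are built from data averaged over a baseline period and over months 4 to 18 after the biologic is started. The synopsis also allows a continuous change in exacerbation frequency as an alternative primary analysis.

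**The concern.** **Target.** Complete response is not an endpoint and has no criteria anywhere in the documents. Taken literally, 6.3 groups partial responders with non-responders, the opposite of the pooling chosen in section 4.1. The predicted probabilities would then describe none of the Table 1 outcomes. The group the study most wants to find, the non-responders, would be mixed with patients who did benefit. The final model is to be tested on the Calgary data, so its outcome has to be fixed before it is fitted.

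**Measures.** The integrated cumulative AUC and the integrated Brier score are averages over a time axis. They need event times, a censoring rule and a horizon, and the plan gives none. An analyst would have to improvise a substitute for each.

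**Working it through.** The plan has no sample-size calculation or class count to reproduce. The check is a comparison of the sections, followed by illustrative arithmetic.

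**1. Target, side by side**

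- Section 6.3: complete response.
- Synopsis (primary objective and endpoint) and section 3: any reduction against none.
- Section 4.1: partial and complete responders pooled; two classes per endpoint in Table 1.
- Elsewhere, complete response appears only as a background rate in section 2.1, without criteria.

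The 6.3 target is the split that section 4.1 chose not to use.

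**2. Measures against endpoint type**

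- Every Table 1 outcome is binary; the primary alternative is a continuous change. None is a time to event.
- Section 4.1 abstracts biologic start and end dates, so time to discontinuation could be derived, but no endpoint or analysis uses it.
- Harrell's C stays usable. For a binary outcome the comparable pairs are one responder with one non-responder, which makes C the ROC AUC. In a simulated binary outcome (n = 300) both were 0.683.
- The ordinary Brier score is a single number, with nothing to integrate over.

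**3. How many patients would change class (illustration)**

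Inputs: N = 300 for Michigan (section 4.1); complete response c = 0.40 and non-response nr = 0.10 to 0.15 (section 2.1, background figures). All 300 are taken as evaluable, although section 5.2 removes patients without adequate follow-up from the final analysis.

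- Under 6.3: complete = 0.40 × 300 = 120; the rest = 180.
- Under the any-decrease endpoint: non-responders = 0.10 to 0.15 × 300 = 30 to 45; responders = 255 to 270.
- Patients who change class = (1 − c − nr) × N:

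| c | nr | Change class |
|---|---|---|
| 0.40 | 0.10 | 0.50 × 300 = 150 |
| 0.40 | 0.15 | 0.45 × 300 = 135 |
| 0.40 | 0.30 (assumed) | 0.30 × 300 = 90 |
| 0.20 (assumed) | 0.15 | 0.65 × 300 = 195 |

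**4. Precision in Calgary under each target**

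Inputs: 200 patients (section 4.1), the same rates, and an assumed AUC of A = 0.70. With n1 in the event class and n2 in the other, the Hanley-McNeil variance is [A(1 − A) + (n1 − 1)(Q1 − A²) + (n2 − 1)(Q2 − A²)] / (n1·n2), where Q1 = A/(2 − A) = 0.538 and Q2 = 2A²/(1 + A) = 0.576. The 95% half-width is 1.96 × the square root of the variance. The formula is not symmetric, so both choices of event class are shown.

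| Split of 200 | Smaller group as event | Larger group as event |
|---|---|---|
| 20 v 180 (nr 0.10) | 0.133 | 0.106 |
| 30 v 170 (nr 0.15) | 0.111 | 0.091 |
| 80 v 120 (c 0.40) | 0.076 | 0.072 |

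**The case against.** The best reply is that complete response stands in an opening statement of purpose, not in a definition of the dependent variable. The section heading speaks of outcomes in the plural, Table 1 sets the two classes for each endpoint, and complete response has no criteria. On that view the only outcome an analyst could code is the one in Table 1. The measures would need only to lose their integrated form, and the list is open in any case.

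Much of this stands. The phrase may well be a slip, which lowers the practical risk. It does not remove the contradiction, because the body of 6.3 names no other outcome.

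A reader might infer more than the documents support:

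- *That the whole plan has the wrong target.* It does not. The synopsis states the primary cutoff analysis correctly, so the conflict is confined to the 6.3 models.
- *That accuracy would go unmeasured.* Harrell's C is usable and other measures are allowed. Two named items are wrong.
- *That 135 to 150 is a limit or an expected count.* It rests on background rates for patients selected as likely to respond. The documents give no rates by endpoint, and other rates move the count both ways.
- *That the models would fail to find non-responders.* The documents give no predictor performance from which to judge that, and discrimination could be unaffected.
- *That worsened patients are unclassified throughout.* For the primary endpoint the synopsis already places them with those who had no reduction, so there the Table 1 wording only needs aligning. The gap is in the other four rows with the same wording.

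**Conclusion.** The point holds, and 6.3 should be corrected before any model is fitted. Its stated target is undefined and conflicts with the synopsis, section 3 and section 4.1. Two of its three named measures cannot be computed as named for any endpoint. Neither conclusion depends on a numerical assumption.

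The size of the effect does depend on assumptions. With the section 2.1 rates and 300 evaluable patients, 135 to 150 (45-50%) would be labelled differently under the two targets. The other scenarios worked above give 90 and 195. These figures show that the choice of target is not cosmetic; they do not estimate what will happen in this cohort.

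**What to change.** In section 6.3:

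- Replace complete response with the responder/non-responder outcome for each endpoint.
- Define non-response, among patients with evaluable baseline and post-treatment values, as not meeting the Table 1 responder criterion, that is, unchanged or worse. This agrees with the synopsis for the primary endpoint and covers worsened patients in the other rows. The restriction to evaluable patients stops missing data from being counted as non-response.
- Replace the two integrated measures with the ordinary ROC AUC, the ordinary Brier score and calibration (intercept and slope) for binary endpoints, and with R-squared or RMSE for the continuous alternative.
- If complete response is of interest, keep it as an additional outcome with its own definition.

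Align the Table 1 non-responder wording with this definition.

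The cost is SAP wording; the replacement measures are standard output. The downside is precision. At an AUC of 0.70 with 200 Calgary patients and 10-15% non-response, the 95% half-width is about 0.09 to 0.13, depending on which class is treated as the event, against 0.07 to 0.08 for a 40/60 split. Loss of patients without adequate follow-up would widen both.
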